#### **9.9.6. Clinical Laboratory Tests**

Blood samples for serum chemistry and hematology and urine samples (random) for urinalysis and urine drug screening will be collected at the time points specified in the Time and Events Schedule. The investigator must review the laboratory report, document this review, and record any clinically relevant changes occurring during the study in the AE section of the eCRF. The laboratory reports must be filed with the source documents.

The investigator's review of laboratory results should address the exclusion criteria, particularly criterion 18. The investigator should use clinical judgment and provide documented evidence when deemed necessary by the medical monitoring team that the subject does not have "ongoing hepatic, renal, cardiac, vascular, pulmonary, gastrointestinal, endocrine, hematologic, rheumatologic, psychiatric, or metabolic conditions" that are significant in the clinical trial setting. Abnormal laboratory results may be repeated to rule out worsening abnormalities and, in

consultation with the sponsor's medical monitor, to establish subject eligibility prior to amyloid testing. The sponsor's medical monitor may request additional evaluation (see Attachment 3).

In the case of hepatic enzyme elevations, attempts should be made to establish an etiology of an underlying condition and demonstrate normalization. The sponsor's medical monitor may request additional evaluation (see Attachment 3).

The following tests will be performed by the central laboratory:

### **Hematology Panel**

- hemoglobin
- hematocrit
- red blood cell (RBC) count
- white blood cell (WBC) count with differential
- platelet count

### **Serum Chemistry Panel**

- sodium
- potassium
- chloride
- bicarbonate
- blood urea nitrogen
- creatinine
- glucose
- aspartate aminotransferase
- alanine aminotransferase
- gamma-glutamyltransferase
- total bilirubin
- folic acid (screening only)
- alkaline phosphatase
- creatine phosphokinase
- lactic acid dehydrogenase
- uric acid
- calcium
- phosphate
- albumin
- total protein
- cholesterol
- triglycerides
- magnesium
- Vitamin B12 (screening only)

### **Thyroid Hormones (screening only)**

- thyroid stimulating hormone (TSH)
- thyroxine (T4)
- tri-iodothyronine (T3)

### **Coagulation (screening only)**

- prothrombin time
- activated partial thromboplastin time

**Urinalysis**

Dipstick	Flow Cytometry
-specific gravity	-RBC
-pH	-WBC
-glucose	-epithelial cells
-protein	
-blood	
-ketones	Sediment
-bilirubin	-crystals
-urobilinogen	-casts
-nitrite	-bacteria
-leukocyte esterase	

Dipstick and flow cytometric analysis of the urine samples will be performed in parallel, ie, in the same sample at the same time. If there is discordance between the dipstick results and the flow cytometric results, the sediment will be examined microscopically.

**Serology (screening only)**

-HIV antibody	-hepatitis C virus antibody
-HBsAg	

**Urine Drug Screen** (opiates [including methadone], cocaine, amphetamines, methamphetamines, barbiturates, and benzodiazepines)

**9.10. Sample Collection and Handling**

The PK, PD (biomarker), and genomic sampling times and sampling volumes can be adapted without protocol amendment provided that the specified maximal volume collected per subject will not be exceeded. Refer to the Time and Events Schedule for the timing and frequency of all sample collections.

The actual dates and times of blood and CSF sample collection will be recorded to the nearest minute in the source documentation, on the laboratory requisition form, and/or in the eCRF. If blood samples are collected via an indwelling cannula, an appropriate amount (1 mL) of serosanguineous fluid slightly greater than the dead space volume of the lock will be removed from the cannula and discarded before each blood sample is taken. If a mandarin (obturator) is used, blood loss due to discard is not expected.

Instructions for the collection, handling, storage, and shipment of samples are found in the laboratory manual. Collection, handling, storage, and shipment of samples must be under the specified, and where applicable, controlled temperature conditions as indicated in the laboratory manual. Additional details for the optional immunologic substudy for T-cell response will be provided in a laboratory manual.

## 10. SUBJECT COMPLETION/WITHDRAWAL

### 10.1. Completion

A subject will be considered to have completed the treatment phase of the study if he or she has completed assessments at Month 54 of the double-blind treatment phase. Subjects who prematurely discontinue study treatment for any reason before completion of the double-blind treatment phase will not be considered to have completed the study.

### 10.2. Discontinuation of Study Treatment

If a subject's study treatment must be discontinued before the end of the treatment regimen, this will not result in automatic withdrawal of the subject from the study.

Subjects who discontinue study treatment prematurely will be asked to complete all regular study visits through the end of the study. To reduce burden on subjects and increase compliance, the focus will be on collecting primary and secondary clinical outcome measures and reducing other assessments in these subjects.

Subjects who meet the criteria for discontinuation of study treatment should have the event reported as an SAE and should follow the SAE reporting as outlined in Section 12.3.2.

A subject's study treatment will be discontinued if the investigator believes that for safety reasons (eg, AE) it is in the best interest of the subject.

For subjects during the first 3 months of treatment with study drug, treatment must be discontinued if any of the following occurs (for details see Attachment 3):

- ALT or AST  $>5 \times \text{ULN}$
- ALT or AST  $>3 \times \text{ULN}$  and total bilirubin  $>2 \times \text{ULN}$  or International Normalized Ratio (INR)  $>1.5$
- ALT or AST  $>3 \times \text{ULN}$  with the appearance of fatigue, nausea, vomiting, right upper quadrant pain or tenderness, fever, rash, and/or eosinophilia  $>5\%$

For subjects that have completed 3 months of treatment with study drug, treatment must be discontinued if any of the following occurs (for details see Attachment 3):

- ALT or AST  $>8 \times \text{ULN}$
- ALT or AST  $>5 \times \text{ULN}$  for more than 2 weeks
- ALT or AST  $>3 \times \text{ULN}$  and (total bilirubin  $>2 \times \text{ULN}$  or INR  $>1.5$ )
- ALT or AST  $>3 \times \text{ULN}$  with the appearance of fatigue, nausea, vomiting, right upper quadrant pain or tenderness, fever, rash, and/or eosinophilia ( $>5\%$ )

Note: Abnormal liver enzymes greater than  $3 \times \text{ULN}$  at any time during the treatment phase should be confirmed within 24-72 hours (See Attachment 3).

If the subject has a QTcF interval of >500 msec and/or QTcF increase versus baseline of >60 msec, confirmed upon repeat ECG, after consultation with the sponsor's medical monitor, treatment must be discontinued.

Re-initiation of study treatment for subjects with the above described changes in QTcF interval should only be done after consultation with the sponsor medical monitor and in mutual agreement between the sponsor and the study center.

If a subject discontinues study treatment before the end of the double-blind treatment phase and decides not to complete the study procedures, ET and posttreatment assessments should be obtained.

### **10.3. Withdrawal From the Study**

A subject should be withdrawn from the study for any of the following reasons:

- Lost to follow-up
- Withdrawal of consent
- Death
- Noncompliance

If a subject is lost to follow-up, every reasonable effort must be made by the study-site personnel to contact the subject and determine the reason for withdrawal. The measures taken to follow-up must be documented.

When a subject withdraws before completing the study, the reason for withdrawal is to be documented in the eCRF and in the source document. Study drug assigned to the withdrawn subject may not be assigned to another subject.

Subjects who are withdrawn will not be replaced.

For subjects who have cognitive decline during the study, see Section [16.2.3](#).

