During the entire double-blind treatment phase, subjects should self-administer study drug (atabecestat/placebo) on a once daily schedule with a glass of noncarbonated water (approximately 200 mL) preferably in the morning between the hours of 0700 and 1100 (7:00-11:00 AM), according to the instructions provided by the investigator. The first dose of study drug should be self-administered by the subject at the site as described above, and at all subsequent scheduled visits, subjects should self-administer their study medication on-site. Subjects having difficulties reaching the site during morning hours will be permitted to administer drug later during the day (eg, with lunch), but every attempt should be made to ensure consistency in the time of study drug administration during the course of the study.

Subjects who forget to take their daily dose in the morning as directed will be instructed to take their daily dose later that day, as long as it is before 1600 hours (4:00 PM). Subjects who forget to take their morning dose of study drug and cannot take their daily dose of study drug before 1600 hours (4:00 PM) will be instructed not to take any dose during that day and to resume dosing the following day.

Subjects who are no longer capable of ensuring compliance with their daily medication schedule, in the judgment of the investigator (eg, due to progression to dementia), will be required to have support in the handling and administration of study drug (eg, study informant, partner, caregiver, or nurse practitioner).

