## 11.3. Efficacy Analyses

### 11.3.1. Analysis of the Primary Endpoint

The primary objective of this study is to test the hypothesis that either dose regimen evaluated for atabecestat will slow cognitive decline compared with placebo, as measured by the primary endpoint of the PACC change from baseline at Month 54 (see Section 9.3.1).

The primary estimand, the main clinical quantity of interest to be estimated in the study, is defined by the difference in means versus placebo for the primary endpoint in the specified population under the following postrandomization measure of intervention:

- **Population:** amyloid-positive subjects who are asymptomatic at risk for developing Alzheimer's dementia
- **Endpoint:** The Month 54 (Year 4.5) PACC change score (as defined in Section 9.3.1)
- **Measure of Intervention:** the effect of the initially randomized treatment regardless of treatment compliance or initiation of any Alzheimer adjunctive therapy.

The primary analysis will be based on the intent-to-treat analysis set, which includes all randomized subjects. The analysis of the PACC change score will only include subjects for whom the PACC change score is non-missing at least 1 postbaseline time point. Measurements collected after initiation of any Alzheimer adjunctive therapy will be included in the analysis for the primary estimand. Measurements collected after treatment discontinuations due to reasons potentially related to treatment (eg, treatment-related adverse events or lack of efficacy) will also be included in the analysis of the primary estimand. However, measurements collected after treatment discontinuations due to events that are clearly not treatment-related (eg, life events such as relocation, loss of transportation, loss of informant) will not be included in the analysis of the primary estimand.

A mixed effect model for repeated measurement (MMRM) analysis will be performed to assess the treatment effect. The change from baseline in PACC at each visit that the endpoint is measured will be the dependent variable. Visits scheduled for the measure will be treated as a categorical variable with values equal to the visit numbers. An unstructured covariance structure will be assumed. The model for the fixed effects will include the following terms: baseline of the endpoint measure, treatment group, visit, treatment-by-visit interaction, age, sex, education, hippocampal volume, country, and *APOE*  $\epsilon 4$  carrier status.

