4.5. Protocol Deviations

In general, the following list of major protocol deviations may have the potential to impact subjects' rights, safety or well-being, or the integrity and/or result of the clinical study. Subjects with major protocol deviations will be identified prior to database lock and the subjects with major protocol deviations will be summarized by category:

- Developed withdrawal criteria but not withdrawn
- Entered but did not satisfy criteria
- Received wrong treatment or incorrect dose
- Other

A listing of major protocol deviations will be provided.

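### Protocol 10.3 makes undefined noncompliance a reason for study withdrawal, which, if it covers study drug, conflicts with a primary estimand that disregards compliance

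*Protocol*

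**What the plan says.** Protocol Section 10.3 opens its list with "A subject should be withdrawn from the study for any of the following reasons" and gives four entries: loss to follow-up, withdrawn consent, death and "Noncompliance". The last has no definition and no threshold. It does not say whether it means study drug, visits or procedures.

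Other sections point the other way:

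- **Protocol 11.3.1** defines the measure of intervention as "the effect of the initially randomized treatment regardless of treatment compliance or initiation of any Alzheimer adjunctive therapy".
- **Protocol 10.2** says of early stopping of study drug that "this will not result in automatic withdrawal of the subject from the study", and adds: "Subjects who discontinue study treatment prematurely will be asked to complete all regular study visits through the end of the study".
- **Protocol 6** takes up "Subjects who are no longer capable of ensuring compliance with their daily medication schedule, in the judgment of the investigator (eg, due to progression to", where the example named is dementia, and requires that they be given help with handling and taking the drug.
- **Protocol 7** answers poor drug compliance with further instruction and does not mention withdrawal.
- **SAP 4.5** lists "Developed withdrawal criteria but not withdrawn" as a category of major protocol deviation.

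**The concern.** An estimand that disregards compliance needs outcome data from noncompliers. Read literally, Section 10.3 ends their scheduled follow-up. A subject who stops the drug completely is then followed to Month 54, while one who takes it irregularly is removed.

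The other three entries are losses that the trial cannot prevent. Noncompliance is the only one imposed by the plan. In a 4.5-year study of emerging impairment it may also be related to the outcome: Section 6 itself names progression to dementia as a cause, and intolerance is another plausible one. Missing PACC, CFI and CDR scores could then depend on disease course or on treatment. The missing-data sensitivity analyses in Section 11.3.4 are to use follow-up from subjects who stop study medication, and subjects withdrawn from the study cannot supply it.

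**Working it through.** **1. What follow-up remains after withdrawal.** The Time and Events Schedule asks withdrawn subjects for an Early Termination visit. Its footnote k allows PACC there only if it was not done at the previous visit as scheduled. No PACC is marked at the follow-up visit. The Synopsis promises efforts to obtain endpoint efficacy data from dropouts, but Sections 9.1 and 10.3 give no procedure for doing so.

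**2. The plan's own figures (Protocol 11.2.1).** Inputs: 385 completers per arm, 30% attrition, difference 0.49, SD 2.44, constant correlation 0.5, two-sided alpha 0.05, stated power 83%.

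- Randomized per arm: 385 / (1 − 0.30) = 550, which matches.
- Power on the stated MMRM basis, with nine PACC visits (Months 6 to 54) and retention falling to 70%: add up the inverse correlation matrices of the dropout patterns, each weighted by its share of subjects, and take v as the Month 54 element of the inverse of that sum. Then SE = 2.44 × √(2v/550) and power = Φ(0.49/SE − 1.96). The effective number per arm, 550/v, is 431 to 437 and power is 83.8% to 84.3%. The dropout shapes (linear and exponential) are assumed. This agrees with the stated 83% to within about one point.
- A plain two-sample comparison of 385 per arm gives 79.6%, so the stated figure depends on the MMRM basis.

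**3. Effect on power.** The 30% allowance is 0.30 × 550 = 165 subjects per arm, all causes together. If noncompliance withdrawals are among them, power does not change. If they come on top (assumed values):

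| Extra attrition | Completers per arm | MMRM power | N per arm to keep 385 completers |
|---|---|---|---|
| 0 | 385 | 83.8–84.3% | 550 |
| 2 points | 550 × 0.68 = 374 | 83.1–83.6% | 385/0.68, rounded up: 567 |
| 5 points | 550 × 0.65 = 357.5 | 81.9–82.5% | 385/0.65, rounded up: 593 |
| 10 points | 550 × 0.60 = 330 | 79.6–80.4% | 385/0.60, rounded up: 642 |

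**4. Direction of bias.** All rates and deficits here are assumptions.

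- If withdrawn subjects would later score D units below the rest, the difference among those retained is the true difference + (active share − placebo share) × D, before any recovery through the MMRM. With 4% active, 6% placebo and D = 2 to 4, the change is −0.02 × 2 to 4 = −0.04 to −0.08. With the shares reversed it is +0.04 to +0.08.
- If a fraction q of the active arm is withdrawn and truly gets no benefit, while a missing-at-random model credits them with the full 0.49, the estimate is too high by 0.49 × q: 0.01, 0.02 and 0.05 for q = 2%, 5% and 10%.

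Plausible mechanisms therefore push in opposite directions, and the documents do not say which would dominate.

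**The case against.** The strongest reply is that the conflict rests on an assumed meaning. Section 10.3 governs leaving the study, drug stopping has its own section, and Section 10.2 uses the word compliance in connection with the burden of visits and assessments. If noncompliance means missed visits or procedures, the estimand wording is not contradicted. That reading is possible but not stated, and it would still remove subjects whose remaining visits could have been collected.

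A second reply is that the more specific text favours retention. Section 6 requires support, Section 7 re-education, and Section 9.1.3 every attempt to follow subjects to Month 54. Section 10.3 itself sends subjects with cognitive decline to Section 16.2.3, which provides for renewed consent or assent. This makes removal of a declining subject less likely. It does not remove the instruction in the list.

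Several stronger readings are tempting, and the documents do not support them:

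- **All later PACC data are lost.** A conditional Early Termination PACC and the Synopsis commitment to retrieve endpoint data stand against this, although the commitment has no procedure.
- **Every withdrawn subject's later data belong in the estimand analysis.** Section 11.3.1 itself leaves out "measurements collected after treatment discontinuations due to events that are clearly not treatment-related".
- **The bias is 8–16% of the planned effect.** That is 0.04 to 0.08 divided by 0.49, and every input is assumed. A deficit of 2 to 4 units exceeds the whole 1.40-unit amyloid-related difference and is 0.8 to 1.6 SD (2/2.44 to 4/2.44). The sign is also unknown.
- **SAP 4.5 pushes sites to remove subjects.** It is a general reporting category that does not name noncompliance and gives sites no instruction. This SAP version was also written because dosing had stopped.

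**Conclusion.** The point holds as an inconsistency in the protocol's confirmatory design. It is a direct conflict with the estimand if noncompliance includes study-drug noncompliance. On the narrower reading it is an avoidable loss of outcome data. The loss may be informative, but its direction and size cannot be computed because the documents give no noncompliance rate. Power is unaffected within the 30% allowance and falls to about 80% only under an assumed ten extra points.

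A reader might infer that the analysis now planned is damaged. It is not on this ground. SAP 1.3 rules out formal hypothesis testing, and SAP 5.2.1 specifies no primary estimand and leaves PACC after treatment discontinuation out of the on-treatment analysis. SAP Section 1 reports that no subject had more than 27 months of treatment when dosing ceased, so the Month 54 comparison will not take place.

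**What to change.** Reconcile Protocol 10.3 with Sections 6, 7, 10.2 and 11.3.1. Remove noncompliance from the reasons for study withdrawal. State that a subject who is noncompliant with study drug or with individual visits stays in the study for outcome follow-up as in Section 10.2, unless the subject withdraws consent, dies or is lost to follow-up. Covering both meanings settles the ambiguity. Make no change to the study-drug stopping rules.

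It follows that such retained subjects would not count under "Developed withdrawal criteria but not withdrawn" in SAP 4.5; one clarifying line there is enough.

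The cost is one protocol bullet, one sentence and one SAP line. The downside is small: sites keep scheduling visits for less reliable subjects, and those visits are already planned.

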### **Withdrawal from the Use of Samples in Future Research**

The subject may withdraw consent for use of samples for research (refer to Section [16.2.5](#)). In such a case, samples will be destroyed after they are no longer needed for the clinical study. Details of the sample retention for research are presented in the main ICF.

## **11. STATISTICAL METHODS**

Statistical analysis will be performed by the sponsor or under the authority of the sponsor. A general description of the statistical methods to be used to analyze the efficacy and safety data is outlined below. Specific details will be provided in the SAP.

## 11.1. Subject Information

For all subjects who are randomly assigned to study drug and receive at least 1 dose of study drug, descriptive statistics will be provided.

## 11.2. Sample Size Determinations

### 11.2.1. Primary Cognitive Endpoint

The decline in PACC from baseline was assessed using data from clinically normal populations in the Alzheimer's Disease Neuroimaging Initiative (ADNI), Australian Imaging, Biomarkers, and Lifestyle Flagship Study of Aging (AIBL), and ADCS Prevention Initiative studies. The average difference in PACC decline at 36 months in AIBL between subjects with and without elevated brain amyloid was 1.40 units (95% CI: 0.52 to 2.29), and the SD at Week 144 (Month 36) was estimated at 2.44 units. If a similar decline in PACC at Month 54 is seen and the SD is 2.44, then 385 completers per treatment arm would provide 83% power (at the 2-sided alpha of 0.05) to detect a difference from placebo of 0.49. The SD at 54 months will likely be higher. If the SD at month 54 increases by 20% to 2.93, then 555 completers per groups would be required in order to maintain the same power. The sample size is estimated based on an MMRM model, assuming a constant correlation of 0.5. Under the above assumptions and assuming the attrition is no more than 30%, a total of 1,650 randomized subjects (550/treatment arm) will be required at minimum, and 2,400 subjects (800/treatment arm) at maximum. The treatment difference of 0.49 represents 35% of the 1.40-unit difference, or a 35% slowing of decline in PACC in subjects with elevated brain amyloid. If the average time from amyloid positivity to dementia is 15 years, then, assuming linear decline, a 35% slowing of cognition may translate into approximately a 5-year delay in the onset of dementia. A 5-year delay could lead to a 57% reduction in the number of patients with dementia.

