### **STATISTICAL METHODS**

#### *Sample Size Determination for Primary Endpoint*

The decline in PACC from baseline was assessed using data from clinically normal populations in the Alzheimer's Disease Neuroimaging Initiative (ADNI), Australian Imaging, Biomarkers, and Lifestyle Flagship Study of Aging (AIBL), and ADCS Prevention Initiative studies. The average difference in PACC decline at 36 months in AIBL between subjects with and without elevated brain amyloid was 1.40 units (95% CI: 0.52 to 2.29), and the SD at Week 144 (Month 36) was estimated at 2.44 units. If a similar decline in PACC at Month 54 is seen and the SD is 2.44, then 385 completers per treatment arm would provide 83% power (at the 2-sided alpha of 0.05) to detect a difference from placebo of 0.49. The SD at 54 months will likely be higher. If the SD at month 54 increases by 20% to 2.93, then 555 completers per

groups would be required in order to maintain the same power. The sample size is estimated based on an MMRM model, assuming a constant correlation of 0.5. Under the above assumptions and assuming the attrition is no more than 30%, a total of 1,650 randomized subjects (550/treatment arm) will be required at minimum, and 2,400 subjects (800/treatment arm) at maximum. The treatment difference of 0.49 represents 35% of the 1.40-unit difference, or a 35% slowing of decline in PACC in subjects with elevated brain amyloid. If the average time from amyloid positivity to dementia is 15 years, then, assuming linear decline, a 35% slowing of cognition may translate into approximately a 5-year delay in the onset of dementia. A 5-year delay could lead to a 57% reduction in the number of patients with dementia.

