## **2.2. Hypotheses**

[figure not shown]
The primary hypothesis is that cognitive decline, as measured by the PACC change from baseline at Month 54 (Year 4.5), will be significantly less for subjects treated with either atabecestat dose in comparison to subjects treated with placebo. The key secondary hypothesis is that functional decline, as measured by the CFI change from baseline at Month 54 (Year 4.5), will be significantly less for subjects treated with either atabecestat dose in comparison to subjects treated with placebo.

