### **11.3.3. Multiple Comparison Adjustment**

Statistical adjustment will be made to account for multiplicity due to multiple dose comparisons for the primary endpoint and the key secondary endpoint (Section 11.3.1 and Section 11.3.2). To control the Type I error a 2-stage gatekeeping strategy will be employed. In the first stage, the atabecestat dose arms will be compared with placebo on the primary efficacy endpoint using a truncated Hochberg procedure with a 2-sided  $\alpha = 0.05$  and truncation parameter  $\lambda = 0.5$ . If both arms are superior to placebo, both arms will be compared with placebo on the key secondary efficacy endpoint using the usual Hochberg procedure with a 2-sided  $\alpha = 0.05$ . If neither arm is superior to placebo on the primary efficacy endpoint, the procedure will stop and the comparison of each atabecestat arm to placebo on the key secondary endpoint will also be ruled not statistically significant. If 1 of the 2 arms is superior to placebo on the primary efficacy endpoint, that arm will be compared with placebo on the secondary efficacy endpoint using a 2-sided  $\alpha = 0.0125$ . The details of the final multiple comparison procedure will be specified in the SAP.

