1.3. Statistical Hypotheses for Trial Objectives

This section describes the pre-specified statistical hypotheses. However, given the cessation of screening, randomization, and dosing, no formal statistical hypothesis testing will be done.

There are two families of statistical hypotheses: a primary family in which the atabecestat dose groups are compared to the placebo group on the primary efficacy endpoint and a secondary family in which the atabecestat dose groups are compared to the placebo group on the key secondary efficacy endpoint.

The statistical null hypothesis for the primary efficacy endpoint is that there is no difference between either atabecestat dose group and placebo for cognitive decline as measured by the PACC change score at Month 54 (Year 4.5). The alternative hypothesis is that at least one atabecestat dose group is different from placebo for cognitive decline at Month 54 (Year 4.5).

The statistical null hypothesis for the key secondary efficacy endpoint is that there is no difference between either atabecestat dose group and placebo in the decline of cognitive function and performance of everyday activities as measured by the Cognitive Function Index change from baseline at Month 54 (Year 4.5). The alternative hypothesis is that at least one atabecestat dose group is different from placebo in the decline of cognitive function and performance of everyday activities at Month 54.

A gate-keeping strategy combined with a multiple comparison procedure will control overall Type I error over both families of hypotheses at 0.05 (two-sided). Details of the multiple-testing strategy are provided in Section 5.1.1.

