5.1. Analysis Specifications

5.1.1. Level of Significance

At the time of cessation of dosing, 34% of the planned 1650 subjects had been randomized and 80% of those randomized had no more than 12 months of the planned 54 months of treatment. As a result, any statistical comparisons will be considered exploratory in nature and will be performed at the 0.05 level of significance without adjustment for multiple comparisons.

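### The 83% power in Protocol 11.2.1 is for an unadjusted 0.05 comparison; under the protocol's own truncated Hochberg test, power is about 75–78% per dose and about 88% for at least one dose if both work

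*Protocol*

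**What the plan says.** Protocol 11.2.1 assumes a difference from placebo of 0.49 and takes its SD from an external cohort: "the SD at Week 144 (Month 36) was estimated at 2.44 units". On that basis, "then 385 completers per treatment arm would provide 83% power (at the 2-sided alpha of 0.05) to detect a difference from placebo of 0.49". That statement appears again in the Synopsis: "385 completers per treatment arm would provide 83% power (at the 2-sided alpha of 0.05) to detect a difference from placebo of 0.49". SAP 1.4 repeats it too. For an SD 20% larger (2.93), Protocol 11.2.1 asks for 555 completers per arm so that power stays unchanged. It allows for attrition of up to 30%, and so arrives at 1,650 randomized as a minimum and 2,400 as a maximum.

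The primary hypothesis in Protocol 2.2 is that decline "will be significantly less for subjects treated with either atabecestat dose in comparison to subjects treated with placebo". Under Protocol 11.3.3 the two dose arms "will be compared with placebo on the primary efficacy endpoint using a truncated Hochberg procedure", with two-sided alpha 0.05 and truncation parameter 0.5. If only one arm wins, the key secondary endpoint is tested for that arm at 0.0125.

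After the early stop, SAP 1.3 says that "no formal statistical hypothesis testing will be done". SAP 5.1.1 says that any comparisons are "performed at the 0.05 level of significance without adjustment for multiple comparisons".

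**The concern.** The sample size section uses a significance level that the protocol's primary test never applies to a single dose. A dose with a p-value between 0.0375 and 0.05 cannot be declared superior at all. A dose with a p-value between 0.025 and 0.0375 succeeds only if the other dose is also at or below 0.0375. The stated 83% therefore overstates the chance that a given effective dose is declared superior.

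It is not the power of the either-dose hypothesis either. That power lies below 83% if only one dose works and above it if both do. A reader cannot tell whether 83% is meant per dose, for both doses or for at least one, although these differ by some 20 points.

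The amendment history suggests how this arose. Amendment 4 replaced hierarchical testing with gatekeeping, while the log records the last change to the power calculation under Amendment 3. The mismatch itself is between two current sections.

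**Working it through.** **Inputs.** Difference 0.49; SD 2.44 (sensitivity 2.93); 385 (or 555) completers per arm; MMRM with constant correlation 0.5; 30% attrition from 550 per arm (all Protocol 11.2.1). Truncated Hochberg, alpha 0.05, truncation 0.5 (Protocol 11.3.3). Allocation 1:1:1 with a shared placebo arm (Protocol 5), so the two dose contrasts correlate at 0.5.

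**1. The protocol's own figure.** A completers-only comparison has non-centrality 0.49 / (2.44 × √(2/385)) = 2.786, and power Φ(2.786 − 1.960) = 79.6% (79.5% with the t distribution). The named MMRM also uses the earlier visits of dropouts. With 550 randomized per arm, compound symmetry 0.5 and monotone dropout to 70% retained (the pattern is assumed, since the protocol gives none), nine post-baseline visits give an effective 431–437 per arm and 83.8–84.3% power. Three or six visits give 82.1–84.0%. So 83% reproduces for one comparison at unadjusted 0.05. Also 385 × (2.93/2.44)² = 555.

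**2. Critical values under Protocol 11.3.3.**
- Larger p-value: (0.5 + 0.5/2) × 0.05 = 0.0375, z = 2.080
- Smaller p-value: (0.5/2 + 0.5/2) × 0.05 = 0.025, z = 2.241

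The protocol's 0.0125 for the key secondary endpoint when one dose wins is the unspent half of 0.025, which confirms this reading.

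**3. Power under that procedure.** Taking the protocol's 83% as base, the non-centrality is 1.960 + 0.954 = 2.914.
- One dose at 0.025: Φ(2.914 − 2.241) = 74.9%. Under the full procedure with the other dose null: about 75.0%.
- Both doses effective at 0.49, bivariate normal with correlation 0.5: 68.4% for both and 78.3% per dose. At least one is 2 × 78.3 − 68.4, about 88.3%.

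A simulation of 4,000,000 draws agrees. Under the global null the procedure rejects 4.7%, within the 5% family level.

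**4. Sensitivity to the base.**

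| Unadjusted base | Effective dose, other null | Per dose, both effective | At least one, both effective | Both, both effective |
|---|---|---|---|---|
| 79.6% (completers only) | 70.8% | 74.3% | 85.2% | 63.4% |
| 81% | 72.6% | 75.9% | 86.5% | 65.4% |
| 83% (protocol) | 75.0% | 78.3% | 88.3% | 68.4% |
| 84% | 76.3% | 79.5% | 89.1% | 69.9% |

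**5. Size needed to hold 83%.**
- At 0.025, the ratio is ((2.241 + 0.954)/2.914)² = 1.202. At SD 2.44: 385 × 1.202 = 463 completers per arm; 463/0.7 × 3 is about 1,985 randomized, within the cap. At SD 2.93: 555 × 1.202, about 668; 668/0.7 × 3 is about 2,860, above 2,400.
- For 83% per dose with both doses effective, the ratio is 1.117: 430 and 620 completers per arm, or about 1,843 and 2,657 randomized. The second is again above the cap.
- At the cap itself (800 × 0.7 = 560 completers per arm, SD 2.93): 75.5% for one effective dose; if both work, 78.7% per dose, 68.9% for both and 88.5% for at least one.

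**The case against.** **The 83% is not miscalculated, and its alpha is stated.** This stands. The figure reproduces under the named method, and the protocol never says that it is power under Section 11.3.3; reading it as per-dose power is an inference from its wording. But it is the only power given for the primary endpoint, it justifies N, and under Section 11.3.3 neither scenario examined (other dose null, or both doses at 0.49) yields 83%.

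**For the either-dose hypothesis the true figure may be higher.** Also correct, if both doses have the full effect: 88%. That depends on equal effects. Protocol 3.2.3 expects CSF amyloid-beta 1-40 reductions of about 50% at 5 mg and 84% at 25 mg, so equal clinical effects cannot be assumed. If the second dose has half the effect, power is about 76% for the fully effective dose and about 77% for at least one.

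**The cap statement is conditional.** The protocol treats 30% attrition as an upper bound. At 800 per arm, 668 completers are reachable if attrition is at most 16.5%, and 620 if it is at most 22.5%. But 30% is the rate from which the protocol derives its own 800 per arm, so the comparison is like for like. The condition should be stated.

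**The trial stopped and the procedure will not be used.** True, and it limits the consequence to the design record. The protocol remains that record, and SAP 1.4 still repeats the 83% without qualification.

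**Conclusion.** The concern holds. The protocol's sample size statement and its primary test do not match. The fault is an omitted multiplicity adjustment in the power statement, not a slip in computing 83%.

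Against the stated 83%, the planned test gives about 75% per dose (other dose null) to 78% (both doses at 0.49). If both work, it gives about 68% for both and 88% for at least one. These figures take the protocol's rounded 83% as the unadjusted base and a correlation of 0.5 between contrasts. Bases of 81–84% move per-dose power to about 73–80%; the completers-only base gives 71–74%. In every case per-dose power is below its base.

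The correction should be made for the design record. No analysis or result of the stopped trial is affected.

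**What to change.** Keep N. In Protocol 11.2.1 and the Synopsis, replace the power statement with:

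> With 385 completers per arm, power is 83% for a single dose-placebo comparison at an unadjusted two-sided 0.05. Under the truncated Hochberg procedure of Section 11.3.3, power is about 75% if only one dose is effective. If both doses have the 0.49 effect, it is about 78% per dose, 68% for both doses and 88% for at least one dose (contrasts correlated at 0.5; approximate, because the unadjusted 83% is rounded).

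Then add:

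> The scenario with 555 completers (SD 2.93) has the same power under Section 11.3.3. Holding 83% at 0.025 there would need about 668 completers per arm (about 2,860 randomized at 30% attrition), above the 2,400 cap.

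In SAP 1.4, add only that the 83% is not adjusted for the two dose comparisons, with a reference to Protocol 11.3.3.

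The cost is a few sentences, with no change to N or to any analysis. The stated per-dose power becomes less favourable, and the at-least-one-dose power is shown as higher than 83% if both doses work.
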